6.2 Qualitative data

Qualitative data will be subject to content analysis, with the aim of summarising and systematising the data (39). Respondents' answers will be read repeatedly to familiarise the researcher with the data. Deductive analysis will be used to identify barriers and facilitators to behaviour change in response to receiving air quality alerts. The identified factors will be categorised within the components of the COM-B model (29) to facilitate a comparison with previous literature. Triangulation with a member of the research team will be used to validate the themes developed.

7 Consent

As this research uses online surveys, no written consent will be taken. However, all potential participants will be provided with full details in the participant information sheet (PIS), which clearly states that participation is entirely voluntary, and that completing any surveys online will indicate their consent to participate.

The PIS will be made available to potential participants both when first contacted via the app. They will have all the time they want to consider participation, and to get in touch with the researchers for questions and clarifications.

Participants will be also informed that while they can withdraw from participation at any time, once they have submitted their answers, they will not be able to withdraw their data.

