4 RESEARCH QUESTION/AIM(S)

The purpose of the present study is to test whether theory and evidence-based alternative communication formats, targeting message specificity and previously identified psychosocial predictors of adherence, could improve the behavioural impact of existing alert systems, compared to the official messages sent in association with the UK AQIs.

Research questions

Primary questions:

1) What is the main effect of using behaviourally enhanced messages, compared to the currently used DAQI messages, to present the health advice associated with air quality notifications for a hypothetical high air pollution scenario on adherence intentions?

Prediction:

A) The behaviourally enhanced messages will lead to stronger intentions to adhere to recommendations.

2) What is the main effect of using a behaviourally enhanced message, compared to the currently used DAQI messages, to present the health advice associated with air quality notifications on actual behaviour changes at four weeks?

Prediction:

A) The enhanced messages will lead to greater behaviour changes.

3) In case of a real alert being issued during the study period, how do the different messages affect actual behaviour change?

Prediction:

A) The enhanced messages will lead to greater behaviour change.

Secondary questions:

4) If there is a format effect, which variables mediate the relationship between the information format and behaviour change?

5) Which factors are associated with greater behaviour change across all groups?

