	Actual Behaviour change ^c	In response to receiving the air quality alert: 
 - I reduced length or level of my physical activity outdoors - I changed my travel route - I changed my exercise location - I changed the time when I travelled - I changed the time when I exercised outdoors - If you answered no, please report the reasons [text box].
	Medication adherence ^c	If you have lung problems: 
 - I used my preventer inhaler daily - I carried my reliever inhaler with me when going outdoors. - If you answered no, please report the reasons [text box].
Final Online Questionnaire – at 4 weeks	Behaviour change at 4 weeks ^b	- In the past 4 weeks, how often have you taken action to reduce exposure to air pollution, I response to hearing or reading an air quality forecast?
	Physical activity ^d	- To stay healthy, the NHS recommends at least 150 minutes of moderate physical activity (e.g. cycling, fast walking, swimming) every week (e.g. 30 minutes 5 days a week). Based on this, how physically active were you in the last week? ^e
	Action planning	
 - In the last 4 weeks, to reduce your exposure to air pollution, have you considered making permanent changes to your daily travel route or exercise place and time?^c - In the last 4 weeks, how often have you checked air quality information before doing physical activity outdoors?^b
	Worry ^a	Adapted from Witte et al. (34) 
 - The information received through the CityAir app made me worry about the possibility of suffering health effects from exposure to air pollution

	- The information received through the CityAir app made me nervous and tense about the possibility of suffering health effects from exposure to air pollution
Severity ^a	Adapted from Witte et al. (34)
	- Air pollution is a severe threat to my health
Conditional susceptibility ^f	- How likely do you think you are to suffer from health effects due to air pollution if you do not take any action to reduce exposure? - How likely do you think people of your same age and sex are to suffer from health effects due to air pollution if they do not take any action to reduce exposure?
Response efficacy ^a	Adapted from Witte et al. (34)
	- Following the health advice received through the CityAir app is effective in protecting me from exposure to air pollution

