Medication response efficacy ^a	If you have lung problems: - Taking my preventer medications daily is effective in helping me to control my asthma - Carrying my reliever medication with me is an effective way to protect my health
Self-efficacy ^a	Items adapted from Witte et al (34) and Rhode et al (35)
	- I am confident I would be able to follow the health advice received through the CityAir app, if I wanted to
Medication self-efficacy ^a	Items adapted from Witte et al (34) and Rhode et al (35)
	- If you have lung problems: I am confident I would be able to take my preventer inhaler every day , if I wanted to - I am confident I would be able to remember to carry my reliever inhaler with me during days of poor air quality, if I wanted to
Response costs ^a	- I do not have enough time to follow the health advice received through the CityAir app - Taking side roads makes my journey too long
Medication response costs ^a	If you have lung problems: - Using the preventer inhaler daily is not safe - Using the preventer inhaler daily makes me dependent on it
Unwanted consequences of intervention ^a	- In the last 4 weeks I stopped exercising altogether due to receiving alerts about poor air quality - In the last 4 weeks, I made an emergency /unplanned visit to A&E or visited my GP due to symptoms caused by air pollution
Sensory cue prevalence ^a	- I trust my own perception of air quality more than any official air quality alert
Credibility ^g	- Meyer's credibility index (36,37) (α=.67)
Clarity ^h	- Overall, how clear were the messages received?
Perceived informed choice ^a	- I received enough information to make an informed choice on how to reduce my exposure to air pollution
Intentions ^a to adopt protective behaviour in response to hypothetical, high air pollution alert	[After reading again the high air pollution hypothetical scenario and tailored advice] - I intend to follow the recommendations received with the air alert to reduce exposure to air pollution - I will avoid going outdoors - I intend to reduce length or level of my physical activity outdoors - I intend to change my travel route - I intend to change my exercise location - I intend to change the time when I travel - I intend to change the time when I exercise outdoors

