Medication adherence intentions ^a	If you have lung problems: - I intend to use my preventer inhaler daily - I intend to carry my reliever inhaler with me
Other intentions (not advised behaviours) ^a	- I will wear a mask as a protection from air pollution - I intend to reduce length or level of my physical exercise indoors

Notes: ^a Measured on 9-point scales, where 1=strongly disagree to 9=strongly agree; ^b From 1 Not at all to 9 all of the time; ^c Possible answers: yes, no, not sure; ^d From 1 Not at all, to 7 more than 150 minutes; ^e Possible answers: Low, Moderate, High, Very High, Not sure, I did not receive any alert; ^f From 1=not at all likely to 9=extremely likely; ^g on a 5-point scale; ^h 1= not clear at all to 9= extremely clear. Demographic data will be collected for all the participants in the first questionnaire.

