6. STATISTICAL ANALYSES

6.1 Quantitative data

ANCOVAs will be performed for all the intentions measures in relation to the high air pollution hypothetical scenario, adjusting for baseline measures collected about one month earlier (target population and intervention/control group entered as fixed factors). Both main and interaction effects will be tested. ANCOVAs will also be performed for the actual behaviour change at 4 weeks (with the intervention/control group entered as fixed factor). These latter analyses will also be ran in the subgroups of healthy and at-risk participants. Chi square tests will be performed to analyse differences in proportion of self-reported actual behaviour change between groups, in relation to a real moderate air pollution episode. A two-way MANOVA (1000 bootstraps) will test whether there are differences between groups (both main effects and interactions) in perceived susceptibility, worry, severity, perceived response efficacy, perception of time, self-efficacy, trust, clarity, credibility and perceived informed choice measures. Multiple linear regressions will be used to assess the associations between main predictor variables and self-reported behaviour change at 4 weeks. Mediations effects of predictor variables on significant behavioural changes will be tested using PROCESS macro (38).

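### Section 6.2 sets out to identify both barriers and facilitators, but the only free-text prompts shown ask for reasons for not acting

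*Combined protocol and SAP*

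**What the plan says.** Section 6.2 of the combined protocol and SAP states the aim of the qualitative work: "Deductive analysis will be used to identify barriers and facilitators to behaviour change in response to receiving air quality alerts". It then gives the use to which the results will be put: "The identified factors will be categorised within the components of the COM-B model (29) to facilitate a comparison with previous literature".

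The material for that analysis comes from the questionnaires summarised in Table 4 (section 5.6). In the alert-period questionnaire, five behaviour items and, for people with lung problems, two inhaler items are each answered on the scale "Possible answers: yes, no, not sure". Each of the two blocks ends with the same prompt: "If you answered no, please report the reasons [text box".

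Section 4 treats the alert itself as contingent. Research question 3 asks: "In case of a real alert being issued during the study period, how do the different messages affect actual behaviour change".

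Separately, the final questionnaire holds closed ratings of possible determinants, for example the self-efficacy item "I am confident I would be able to follow the health advice received through the CityAir app, if I wanted to". Section 6.1 handles such measures quantitatively: "Multiple linear regressions will be used to assess the associations between main predictor variables and self-reported behaviour change at 4 weeks".

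**The concern.** A qualitative analysis can only report what respondents were given room to say. Section 6.2 promises two kinds of finding, what hinders action and what helps it, and the prompts shown ask for the first kind only. The trial tests whether better messages prompt people to act, so those who acted are the most direct source on what helped.

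The planned comparison with earlier literature is also affected. The sponsor's own review (section 1.1.4) notes that some earlier studies asked for reasons on both sides, for following advice and for not following it. Table 1 includes enabling factors such as advice from a GP, local media coverage and smartphone applications. If the trial gathers only reasons for not acting, any facilitators it reports would be chance remarks or barriers turned round. Reversal is weak evidence: that lack of time stops some people does not show that having time is what moved others.

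**Working it through.** No formula applies and the plan states no figure to reproduce. The check sets the stated aim beside every item listed in Table 4.

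| Questionnaire | Closed items | Free-text prompts | Prompts asking why someone acted |
|---|---|---|---|
| First | Intentions, past behaviour, planning, physical activity, symptoms | 0 | 0 |
| Alert period | Alert recall; 5 behaviour items; 2 inhaler items | 2 (one per block, both tied to 'no') | 0 |
| Final, 4 weeks | Behaviour, planning, physical activity, beliefs, message ratings, intentions | 0 | 0 |
| **Total** | | **0 + 2 + 0 = 2** | **0** |

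1. *Who is asked.* The items allow three answers, and only 'no' leads to a prompt. A respondent with no 'no' in a block has nothing to explain there. A respondent with a mixture can reach the box, but it asks about the behaviours not adopted.

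2. *What is asked.* Neither prompt asks what helped, prompted or enabled action. A facilitator could be mentioned in passing, but none is elicited.

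3. *Which behaviour a reason refers to.* As laid out, a single prompt follows five behaviours. The table does not show whether the online form repeats it for each item or asks respondents to name the behaviour.

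4. *When it is asked.* Both prompts sit in the alert-period questionnaire. Research question 3 and section 5.4.1 both speak of a real episode as something that may or may not happen. If none does, no listed item supplies text for section 6.2.

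5. *Other sources.* No interview or focus group is described as a data source.

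**The case against.** The strongest reply is that facilitators are measured, only elsewhere. All participants are to receive the final questionnaire, whether or not they acted. It rates response efficacy, self-efficacy, costs of responding, credibility, clarity and informed choice. Section 6.1 relates predictors to behaviour change by regression, tests mediation, and compares the groups on many of these ratings by MANOVA. This stands. A reader might infer that the trial collects no facilitator data at all, and the documents do not support that. The reply does not rescue section 6.2, however, which is a separate analysis of respondents' own answers. The closed items cover only factors chosen in advance, include nothing on GP advice or local media, and are not tied to the response to a particular alert.

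Three further replies also hold:

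- A reader might infer that people who acted are asked nothing. As laid out, someone who changed route but not exercise time has a 'no' answer and can reach the box.
- A reader might infer that the two arms can no longer be compared on what made action possible. Section 6.2 plans no qualitative comparison between arms, and section 6.1 compares them quantitatively.
- Table 4 is headed as a summary, so the full form may hold other open items. None is shown, and if one exists the protocol should say so.

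On alert dependence, section 5.4.1 extends moderate alerts to the general population group for the study. That gives this group more occasions to receive an alert but does not guarantee one.

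**Conclusion.** The point holds for the qualitative strand. Of the two free-text prompts shown, none elicits reasons for acting, so the facilitator half of the analysis in section 6.2 has no direct data source. Without a real alert, the whole of section 6.2 has no listed source. Both statements assume that Table 4 shows every open item.

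The size cannot be put as a share of respondents. A reader might take the 36% median adherence in section 1.1.5 as the proportion who go unasked. That figure is a median over earlier studies of avoiding, reducing or rescheduling outdoor activity, with a range of 9.7% to 70.7%. It is not an assumption of this trial or a rate for each of its five behaviours. Who reaches the box depends on the joint pattern of answers, which the documents do not give.

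The consequence is limited. No research question in section 4 depends on the free text, and the primary comparisons are unaffected. The point still merits action because a stated analysis cannot be delivered in full as written, and the reasons people had for acting on an alert are hard to recover once the survey has closed.

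**What to change.** In Table 4, after the behaviour items and again after the medication items, add an optional prompt: *If you answered yes to any, what helped or prompted you, and for which behaviour? [text box]*. Asking for the behaviour also lets each reason be linked to the action it explains.

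Optionally, add one open item to the final questionnaire on what helped or hindered action, so that section 6.2 has material even if no alert is issued.

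If neither is wanted, remove facilitators from section 6.2 and limit its conclusions to barriers. If the full questionnaire already contains such an item, list it in Table 4.

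The cost is two optional text boxes in an online form (three with the final item), a slightly longer questionnaire and a little more coding. The quantitative analyses need no change.

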8 ETHICAL AND REGULATORY CONSIDERATIONS

8.1 Assessment and management of risk

As part of the study participants will be presented with one of two versions of health advice associated with real-time air quality notifications. All registered users who accept to take part in the study will receive real-time air quality notifications as usual. The control group will receive associated health advice in the usual format,

whilst the intervention group will receive advice in an alternative format. Which version of the advice they are given will be determined by random. Because we do not want to bias participants, we will not tell them exactly which parts have been changed. In line with the same need to avoid biasing participants, we will withhold one of the details of the hypothesis under test (i.e., that we want to specifically test whether the change in wording will have an impact on their intention and actual responses to the information received).

We have no reasons to believe that this may lead to any discomfort or known risks. However, to obviate any potential risk arising from this, we will provide a debriefing at the end of the study (via the online survey or via the app) and provide participants with all the researchers' contact details for doubts or concerns. The debriefing will explain the study hypotheses, methods and potential implications, and thank them for their contribution.

8.2 Research Ethics Committee (REC) review & reports

- Ethics approval granted by the BDM Research Ethics Panel at King's College London on the 2nd March 2017 [ref: LRS-16/17-4286].
- All correspondence with the REC will be retained.

8.4 Patient & Public Involvement

All research materials and questionnaires will be reviewed by experts from the ERG, and tested through Patient and Public Involvement (PPI) workshops. In particular, members of a PPI panel will review the Participant Information Sheet, the study procedure and participants' proposed involvement, and all the study material that the participants will read.

8.7 Data protection and patient confidentiality

In accordance with the UK Data Protection Act 1998, to the best of our ability, participants' answers in this study will remain confidential. The questionnaires are anonymous – we will not ask for participants' name. We will be using the data from participants in aggregate. The responses of individual participants cannot be identified, and any reports or publications from this research will provide only broad descriptions of the sample, for example, noting the age, gender, ethnicity, occupation and health status.

As with any online related activity the risk of a breach is minimal but always possible, however we will minimize any risks by storing electronic data in a secure password-locked computer files. No data will be accessed by anyone other than the research team. Anonymity of the material will be protected by using anonymous participant ID numbers. Any electronic data containing sensitive confidential data (including email addresses) will be stored in password-protected files in King's College computers and deleted after data collection is complete.

9 DISSEMINATION POLICY

The research data will be used for publication in DD's PhD thesis, in scientific journals, and conferences. This will be clearly stated in the Participant Information Sheet.

